2.7.3 Handling of missing values/censoring/discontinuations

Missing values of secondary endpoints will not be replaced.

2.8 Safety analyses

The secondary safety objective and endpoint of this study is as follows:

To evaluate the safety and tolerability of brolucizumab

- Incidence of Ocular and Non-ocular AEs up to week 52

There are no formal safety hypotheses in this study. All safety analyses will be performed using the Safety Set. All listings and tables will be presented by treatment arm.

Safety endpoints are based on the variables from safety assessments which include:

- Extent of exposure
- Adverse events
- Ophthalmic examination and imaging
- Vital signs

Safety summaries (tables, figures) include only data from the on-treatment period with the exception of baseline data which will also be summarized where appropriate (e.g. change from baseline summaries). In addition, a separate summary for death including on treatment and post treatment deaths will be provided. In particular, summary tables for adverse events (AEs) will summarize only on-treatment events, with a start date during the on-treatment period

(treatment-emergent AEs). Separate summary tables will be provided for AEs of study eye, fellow eye and non-ocular AEs.

2.8.1 Adverse events (AEs)

A treatment-emergent adverse event is defined as any adverse event that develops after initiation of the study treatment or any event already present that worsens following exposure to the study treatment. Only treatment-emergent adverse events will be presented in the summary tables.

All information obtained on adverse events will be displayed by treatment arm and subject. The number (%) of subjects with treatment emergent adverse events (events started after the first dose of study medication or events present prior to start of treatment but increased in severity based on preferred term) will be summarized in the following ways:

- by treatment, primary system organ class and preferred term.
- by treatment, primary system organ class, preferred term and maximum severity.

Separate summaries will be provided for study medication related adverse events, death, serious adverse events, other significant adverse events leading to discontinuation.

Adverse events will be coded using the MedDRA dictionary and presented by system organ class (SOC) and preferred term (PT). Treatment-emergent AEs will be analyzed based on the number and percentage of patients with at least one AE in the category of interest.

Separate presentations will be provided related to ocular events in the study eye and fellow eye and non-ocular (systemic) events.

Additional summaries will be provided by severity and causality (separately assessed for the injection procedure and the drug). Serious adverse events, adverse events leading to discontinuation of study treatment and adverse events related to Covid-19 will also be summarized separately.

In addition, separate listings will be provided for AEs with a start date prior to on-treatment period and AEs after on-treatment period.

2.8.1.1 Adverse events of special interest / grouping of AEs

No adverse events of special interest are defined.

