- **Posterior segment (indirect fundus) examination** will be conducted by the investigator at the screening visit for both eyes. An examination of the peripheral retina must also be conducted to ensure that the intravitreal injection can safely be performed. Posterior segment examination must be performed carefully after pupil dilation before each study treatment. The results of the examination including any abnormalities (e.g. vitreous cells/haze, retinal tear/detachment, hemorrhage and vascular occlusion, vasculitis, etc.) should be recorded in the source documents. If there are any signs of IOI, vitreous cells and haze should be assessed using National Institutes of Health (NIH) grading system (Nussenblatt et al., 1985). The outcome of the examination will be documented in the source document (e.g., ophthalmic examination tool) and appropriate eCRF page as applicable.

Pupil dilation for slit lamp examination and indirect ophthalmoscopy is recommended.

Clinically significant abnormalities of either eye will be recorded on the medical/ocular history page before baseline and on the adverse event page of the eCRF for any findings identified after baseline.

[figure not shown]
Instruct the patient to contact the site for any changes in vision or any symptoms of inflammation between scheduled visits. Every effort should be made to bring the subject for immediate examination.

[figure not shown]
Imaging: When intraocular inflammation, retinal vasculitis, and/or retinal artery occlusion (RAO) is present or suspected during a visit, investigators must perform thorough ophthalmic examination, and will conduct OCT, fluorescein angiography and color fundus photography (preferably wide-field or with peripheral sweeps). These additional assessments will be documented in the source and appropriate eCRF pages as applicable. The images are requested to be uploaded onto the CRC portal. In patients developing intraocular inflammation, including retinal vasculitis and/or retinal vascular occlusion, treatment with brolucizumab in the FALCON study should be discontinued and the events should be promptly managed.

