9.2 Study completion and post-study treatment

Study completion for an individual patient is defined as when the patient finishes his/her study completion / EOS visit, and any repeat assessments associated with this visit have been documented and followed-up appropriately by the investigator or, in the event of an early study termination decision, the date of that decision.

After study completion the subject may receive standard of care or other treatments, at the discretion of the investigator and/or referring physician, if needed.

10 Safety monitoring and reporting

Subjects should be closely monitored for adverse events.

For adverse events of special interest, intraocular inflammation, including retinal vasculitis and/or retinal vascular occlusion please ensure compliance with the following:

- Instruct the patient to contact the site immediately for any changes in vision or any symptoms of inflammation independently of scheduled visits (refer to the optional patient brochure). Every effort should be made to bring the subject for immediate (< 12 hours) examination including on weekends and public holidays.
- Close patient monitoring and thorough examination of the eye should be done to detect potential signs of inflammation ([Section 8.4.3](#)).
- Patients with a medical history of intraocular inflammation and/or retinal vascular occlusion in the year prior to treatment with brolucizumab are at risk of developing retinal vasculitis and/or retinal vascular occlusion and should be closely monitored.
- When IOI, retinal vasculitis, and/or retinal vascular occlusion is present or suspected during any visit, investigators must perform thorough dilated pupil ophthalmic examination, and will conduct OCT, fluorescein angiography and color fundus photography (preferably wide-field or with peripheral sweeps). The images are requested to be uploaded onto the CRC portal.

- If any signs of intraocular inflammation are present, an IVT injection must not be performed. Therefore, investigators must verify that these conditions are not present in the study eye prior to every injection.
- In patients developing intraocular inflammation, including retinal vasculitis and/or retinal vascular occlusion, treatment with brolucizumab in the FALCON study should be discontinued and the events should be promptly managed.

For additional information related to safety assessments refer to [Section 6.7.2](#) and [Section 8.4.3](#).

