12.5.2 Safety endpoints

The secondary safety objective and endpoint of this study is as follows:

To evaluate the safety and tolerability of brolucizumab

- Incidence of ocular and non-ocular AEs up to week 52

There are no formal safety hypotheses in this study. For all safety analyses, the safety set will be used. All listings and tables will be presented by treatment arm.

Safety endpoints are based on the variables from safety assessments which include:

- Extent of exposure
- Adverse events
- Ophthalmic examinations

- Vital signs

Safety summaries (tables, figures) include only data from the on-treatment period with the exception of baseline data which will also be summarized where appropriate (e.g. change from baseline summaries). In addition, a separate summary for death including on treatment and post treatment deaths will be provided. In particular, summary tables for adverse events (AEs) will summarize only on-treatment events, with a start date during the on-treatment period (treatment-emergent AEs). A separate summary table will be provided for AEs of study eye, fellow eye and non-ocular AEs.

The on-treatment period lasts from the date of first administration of study treatment to 30 days after the last administration of study treatment (EOT) or EOS whichever is the latest.

Adverse events

A treatment-emergent adverse event is defined as any adverse event that develops after initiation of the study treatment or any event already present that worsens following exposure to the study treatment. Only treatment-emergent adverse events will be presented in the summary tables.

All information obtained on adverse events will be displayed by treatment arm and subject.

The number (%) of subjects with treatment emergent adverse events (events started after the first dose of study medication or events present prior to start of treatment but increased in severity based on preferred term) will be summarized in the following ways:

- by treatment, primary system organ class and preferred term.
- by treatment, primary system organ class, preferred term and maximum severity.
- by treatment, standardized MedDRA Query (SMQ) and preferred term.

Separate summaries will be provided for study medication related adverse events, death, serious adverse events, other significant adverse events leading to discontinuation.

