2.8.2 Deaths

Deaths and other serious or clinically significant non-fatal adverse events will be listed separately.

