2.8.4.3 Ophthalmic examinations

Pre-injection IOP measurements will be presented descriptively (absolute values and change from baseline). Post-injection IOP measurements will be listed.

Further ophthalmic parameters from slit lamp examination and posterior pole examination (anterior chamber cells/ flares and vitreous cells/ haze) will be presented by frequency tables by visit.

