2.14 Interim analysis

There is no interim analysis planned.

3 Sample size calculation

Due to feasibility reasons, resulting in a substantial delay in recruitment, as described above, with Amendment 2 the recruitment will be prematurely discontinued. A final number of approximately 50 patients is expected to be recruited by the time of approval of the amendment.

As a consequence, all analyses will be performed and interpreted in a purely descriptive manner.

Based on an expected sample size of 25 patients per group, and an assumed common standard deviation of 13 letters, a precision in terms of the width of the respective 95% confidence interval for the difference in change from baseline of the visual acuity of +/- 7,21 can be achieved. Taking into account the current number of patients of (for 23 patients per group), the precision in terms of the half width of the 95% confidence interval would be 7,51.

4 Change to protocol specified analyses

The wording of secondary objective 2) was slightly changed to: "Comparison of proportions of patients maintained at a q12w interval **from baseline / upload to week 52**" instead of per protocol: "Comparison of proportions of patients maintained at a q12w interval **at week 52**".

5 Appendix

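### SAP 2.8.1.1 defines no adverse events of special interest although protocol section 10 names them, and SAP 2.8.1 omits the protocol's SMQ summary without declaring it

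*SAP*

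**What the plan says.** Protocol section 10 introduces its monitoring rules with "For adverse events of special interest, intraocular inflammation, including retinal vasculitis and/or retinal vascular occlusion please ensure compliance with the following". Protocol 9.1.1 lists the same events among the circumstances in which study treatment has to be stopped.

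SAP 2.8.1.1 is the SAP's section for special-interest events and for grouping of AEs. Its only content is "No adverse events of special interest are defined". SAP section 1 states that the SAP is based on protocol version 02 (Amendment 2), which contains the section 10 text.

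Other SAP outputs touch these events:
- SAP 2.8.1 tabulates treatment-emergent AEs by arm, system organ class and preferred term, and again with maximum severity. It adds separate study-eye, fellow-eye and non-ocular presentations, a display by arm and subject, and summaries by causality, seriousness and discontinuation. Its general counting rule is "Treatment-emergent AEs will be analyzed based on the number and percentage of patients with at least one AE in the category of interest".
- SAP 2.8.2 states "Deaths and other serious or clinically significant non-fatal adverse events will be listed separately".
- SAP 2.8.4.3 covers slit-lamp and posterior-pole findings: "anterior chamber cells/ flares and vitreous cells/ haze) will be presented by frequency tables by visit".

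Protocol 12.5.2 lists three treatment-emergent AE summaries. The third is "by treatment, standardized MedDRA Query (SMQ) and preferred term". SAP 2.8.1 repeats the first two only. SAP section 4, which records changes to protocol-specified analyses, contains one item, beginning "The wording of secondary objective 2) was slightly changed to". It concerns the q12w endpoint.

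**The concern.** The two documents disagree on whether special-interest events exist in this trial, and the SAP does not acknowledge the difference. The events are the protocol's main safety issue. Protocol 1.1 describes a causal link between an immune reaction to brolucizumab and RV/RO. Protocol 4.5 says the events were seen more often early in treatment, which is when the arms differ in exposure: three injections by week 8 in the loading arm against one in the non-loading arm.

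The natural descriptive figure is the number of patients per arm with any IOI, RV or RO event. Protocol 4.2 and 4.5 report earlier trials in this grouped form. The readable SAP plans no such figure. If it is assembled afterwards, the choice of which preferred terms count is made with the data in view.

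The SMQ omission is a separate and smaller matter: an output planned in the protocol is absent from the SAP with no record of why.

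**Working it through.** **1. The plan's own figures.** The documents give no safety figure to reproduce. Their only design figures are the BCVA half-widths, which supply the arm sizes used below. With SD 13 and the normal approximation, 1.96 × 13 × √(2/25) = 7.21 and 1.96 × 13 × √(2/23) = 7.51, as stated in protocol 12.8.1 and SAP section 3. This point does not depend on them.

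**2. Does any readable SAP output give patients with any IOI/RV/RO event by arm?**
- Preferred-term tables: no. One patient can appear in several rows.
- Discontinuation summary: no. It should hold most of these cases, given protocol 9.1.1, but mixes them with other AEs.
- Serious or clinically significant AEs (2.8.2): no. This is a listing.
- Cells, flare and haze (2.8.4.3): no. The tables are per visit and record inflammatory signs. They do not cover RV or RO. The grading behind them is itself conditional in protocol 8.4.3: "If there are any signs of IOI, vitreous cells and haze should be assessed using National Institutes of Health (NIH) grading system".
- The counting rule in 2.8.1: it would apply to a group if one were named, but none is.
- Display by arm and subject: the count can be worked out from it by hand, but it is not a planned output.

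**3. Why rows cannot be summed.** If k preferred-term rows in an arm each show one patient, the number of distinct patients lies between 1 and k.

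| k | Distinct patients | % of 25 | % of 23 |
|---|---|---|---|
| 2 | 1 to 2 | 4.0 to 8.0 | 4.3 to 8.7 |
| 3 | 1 to 3 | 4.0 to 12.0 | 4.3 to 13.0 |

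**4. Would there be anything to count?** Illustration only, using grouped rates that the protocol quotes: 3.2% (males) and 5.3% (females) in the two phase 3 trials (protocol 4.5), and 9.3% IOI under q4w dosing beyond loading (protocol 4.2), which is not this trial's regimen. Expected patients = n × p; chance of at least one = 1 − (1 − p)^n.

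| p | Expected, n = 25 | At least one, n = 25 | Expected, n = 23 | At least one, n = 23 |
|---|---|---|---|---|
| 0.032 | 0.80 | 56% | 0.74 | 53% |
| 0.053 | 1.3 | 74% | 1.22 | 71% |
| 0.093 | 2.3 | 91% | 2.14 | 89% |

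**5. Precision of the count.** Exact (Clopper-Pearson) 95% limits: 0/25, up to 13.7%; 1/25, 0.1% to 20.4%; 2/25, 1.0% to 26.0%; 3/25, 2.5% to 31.2%. The table would describe the data and could not compare the arms with any confidence.

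**6. SMQ.** Protocol 12.5.2 has three summaries, SAP 2.8.1 has two, and SAP section 4 has one declared change that is unrelated. The omission is undeclared.

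**The case against.** The strongest reply is that nothing needed is lost. Protocol section 10 uses the special-interest label to introduce site monitoring instructions, and protocol 12.5.2 attaches no analysis to it. The safety endpoint is the incidence of ocular and non-ocular AEs, which the SAP covers. Every event remains visible by preferred term, by eye and by subject, and largely among AEs leading to discontinuation. In about 50 patients, the subject-level display settles the count. At the phase 3 rates, the chance of two or more affected patients in an arm of 25 is only 19% to 39%, so overlapping rows may never arise. Section 10 already fixes the clinical components, leaving only their mapping to preferred terms open.

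Most of this stands, and it rules out several stronger readings:
- A reader might infer that the SAP removed a promised special-interest table. It did not; the grouped count would be an addition.
- A reader might infer that IOI, RV or RO would go unreported. They would not.
- A reader might take the dropped SMQ summary as the intended vehicle for these events. The protocol names no SMQ and does not link it to them.
- A reader might take the counting rule in SAP 2.8.1 as a special-interest rule lacking only its category. The wording is generic and fits organ class, preferred term or severity equally well.

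The reply does not remove the contradiction between the two documents. Nor does it supply a planned patient count, fix the preferred-term mapping in advance, or explain the undeclared SMQ omission.

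**Conclusion.** The point holds in two limited parts. First, SAP 2.8.1.1 contradicts the designation in protocol section 10, and no readable SAP output gives the number of patients per arm with any IOI/RV/RO event. Second, a summary planned in protocol 12.5.2 is missing from SAP 2.8.1 and is not declared in section 4.

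The consequence is confined to descriptive safety reporting; the primary analysis is unaffected. In size, it is an ambiguity such as 1 to 3 patients (4% to 12% of 25) when three single-patient rows appear, against 0.8 to 2.3 expected affected patients per arm of 25. Those expected numbers assume that rates from other trials carry over. The phase 3 patients were treatment-naive and received loading, the 9.3% comes from a different regimen, and the non-loading arm has no matching source.

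Blacked-out SAP entries between 2.11 and 2.14, and protocol 12.6, could not be checked. The change is worth making because it is cheap and resolves a stated conflict, not because validity is at risk.

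**What to change.** Replace the sentence in SAP 2.8.1.1 with text along these lines:

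> IOI, RV and RO (protocol section 10) are grouped by a preferred-term list, or a named SMQ, fixed before database lock. Patients with any of these events, and with each component, will be counted by treatment arm (n, %). Study-eye and fellow-eye events are shown separately, as in 2.8.1. The table is descriptive only.

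The eyes are kept separate because section 10 does not limit the designation to the study eye. If the database is already locked, label the table and its term list as added later.

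Separately, reinstate the SMQ summary in SAP 2.8.1 and name the SMQ, or declare its removal in SAP section 4.

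Cost: one table from AE data already collected, and two SAP wording changes (2.8.1.1, and either 2.8.1 or section 4), plus the SMQ table if it is reinstated.

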2.8.2 Deaths

Deaths and other serious or clinically significant non-fatal adverse events will be listed separately.

2.8.3 Laboratory data

No specific laboratory evaluations for safety assessment will be performed except serum pregnancy testing.

The serum pregnancy test will be conducted for all women of child-bearing potential to assess pregnancy before inclusion into the study at the screening visit. During the study, **urine** pregnancy testing will be performed at visits when serum pregnancy testing will not be

conducted. If a urine test is positive after inclusion in the study, a serum pregnancy test must be performed for confirmation. Results of pregnancy testing will be available as source documentation.

2.8.4 Other safety data

2.8.4.1 ECG and cardiac imaging data

Not applicable.

2.8.4.2 Vital signs

All vital signs data will be listed by treatment arm, subject, and visit/time and if ranges are available, abnormalities (and relevant orthostatic changes) will be flagged. Summary statistics will be provided by treatment and visit/time.

2.8.4.3 Ophthalmic examinations

Pre-injection IOP measurements will be presented descriptively (absolute values and change from baseline). Post-injection IOP measurements will be listed.

Further ophthalmic parameters from slit lamp examination and posterior pole examination (anterior chamber cells/ flares and vitreous cells/ haze) will be presented by frequency tables by visit.

2.9 Pharmacokinetic endpoints

Not applicable.

2.10 PD and PK/PD analyses

Not applicable.

2.11 Patient-reported outcomes

Not applicable.

2.14 Interim analysis

There is no interim analysis planned.

3 Sample size calculation

Due to feasibility reasons, resulting in a substantial delay in recruitment, as described above, with Amendment 2 the recruitment will be prematurely discontinued. A final number of approximately 50 patients is expected to be recruited by the time of approval of the amendment.

As a consequence, all analyses will be performed and interpreted in a purely descriptive manner.

Based on an expected sample size of 25 patients per group, and an assumed common standard deviation of 13 letters, a precision in terms of the width of the respective 95% confidence interval for the difference in change from baseline of the visual acuity of +/- 7,21 can be achieved. Taking into account the current number of patients of (for 23 patients per group), the precision in terms of the half width of the 95% confidence interval would be 7,51.

4 Change to protocol specified analyses

The wording of secondary objective 2) was slightly changed to: "Comparison of proportions of patients maintained at a q12w interval **from baseline / upload to week 52**" instead of per protocol: "Comparison of proportions of patients maintained at a q12w interval **at week 52**".

5 Appendix

5.1 Imputation rules

5.1.1 Study drug

If date of injection is missing, date of visit will be imputed.

5.1.2 AE date imputation

For start date:

- If day missing
 - if month/year(start) gt month/year(first injection) than impute max(date of first injection, mdy(month (start date),1,year(start date)))
else impute mdy(month (start date),1,year(start date))

For end date:

- If complete missing than impute date of last injection+30.
- If day missing
 - if month/year(first injection) gt month/year(end date) than impute mdy(month(end date)+1,1,year(end date))-1)
 - if month/year(first injection) le month/year(end date) le month/year(last injection+30) than impute min(date of last injection+30, mdy(month(end date)+1,1,year(end date))-1)
 - if month/year(end date) gt month/year(last injection+30) than date of last injection+30

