2.1.1 General definitions

The term study treatment is used for Brolucizumab 6 mg/0.05 mL.

The baseline visit is defined as day 1/visit 1.

The on-treatment period lasts from the date of first administration of study treatment to 30 days after the last administration of study treatment (EOT) or EOS whichever is the latest.

Calculation of treatment interval:

- “Mean treatment interval from week 8 to week 52”: (last injection – first injection from week 8 on*) divided by (number of injections from week 8 to week 52 -1)

*the first injection from week 8 on could be at week 8 or later.

- “Mean treatment interval in last 24 weeks prior to first brolucizumab injection” will be calculated as: (date of first brolucizumab injection - date of first anti-VEGF pre-treatment within last 24 weeks) divided by number of injections within 24 weeks prior to first brolucizumab injection.

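### The AE start-date rule dates a new event with a missing start day in the month of the first injection to the 1st of that month, so it is classed as pre-treatment; the comparison should include the same month

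*SAP*

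**What the plan says.** SAP 5.1.2 covers an AE start date with month and year known and the day missing. It has two branches:

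- Start month strictly later than the first-injection month: "if month/year(start) gt month/year(first injection) than impute max(date of first injection, mdy(month (start date),1,year(start date" (closing brackets omitted).
- All other cases, including the same month: "else impute mdy(month (start date),1,year(start date" (closing brackets omitted), with no floor at the injection date.

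Three other passages decide what happens to the imputed date:

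- SAP 2.1.1: "The on-treatment period lasts from the date of first administration of study treatment".
- SAP 2.8: "summary tables for adverse events (AEs) will summarize only on-treatment events, with a start date during the on-treatment period".
- SAP 2.8.1: "separate listings will be provided for AEs with a start date prior to on-treatment period".

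SAP 2.8.1 also gives a definition in words: "A treatment-emergent adverse event is defined as any adverse event that develops after initiation of the study treatment". Worsening of an event already present counts as well. SAP 5.1.3 applies the AE rule to concomitant-medication dates without further detail.

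**The concern.** When the start month equals the first-injection month, the strict comparison is false and the second branch applies. The event is then dated to the 1st, which precedes the first injection for every injection date except the 1st itself. A new event that truly began after the injection therefore falls outside the on-treatment period and leaves the treatment-emergent tables, although it meets the SAP's own verbal definition of treatment-emergent. No other rule in the SAP corrects this case.

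The incidence of ocular and non-ocular AEs up to week 52 is a secondary endpoint, and the error can only remove post-injection events from its tables, which is the non-conservative direction for safety. It acts in the first weeks after the first injection. Protocol 4.5 says that intraocular inflammation and related vascular events were seen more often early in treatment. Protocol 10 treats these as events of special interest, but SAP 2.8.1.1 defines none, so no dedicated summary stands behind the general AE tables.

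**Working it through.** **Example.** First injection 15 March 2022; AE start recorded as March 2022, day missing.

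- As written (`gt`): March is not later than March, so the second branch gives 1 March 2022, which is pre-treatment.
- With `ge`: max(15 March, 1 March) = 15 March 2022, which is on-treatment.

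**Is the strict operator intended?** Under `gt`, the 1st of a later month always falls after the first injection, so the injection date can never be the larger argument of `max()`. Over 549 injection dates and the 12 following months each (549 × 12 = 6,588 combinations), `max()` changed the result 0 times. A floor at the injection date has a purpose only if the same month is in that branch.

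**Inputs for the size.** Every first-injection date from 1 July 2021 (the month in which the first patient was recruited, per Amendment 2) to 31 December 2022 (an assumed end). This gives 11 months of 31 days, 6 of 30 and 1 of 28: 341 + 180 + 28 = 549 dates.

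**How often the same-month date is wrong.** 18 of the 549 dates are the 1st of a month and are harmless. The other 549 − 18 = 531 give an imputed date before the injection. With `ge` the count is 0.

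**Exposed onset days per patient.** For an injection on day d (d ≥ 2) of a month with L days, onsets from day d to day L are misdated, which is L − d + 1 days. Summed over d = 2 to L this is L(L − 1)/2: 465, 435 and 378 days for L = 31, 30 and 28.

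(11 × 465 + 6 × 435 + 378) / 549 = 8,103 / 549 = 14.76, or 14.8 days.

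**Share misdated among post-injection AEs with a missing start day.** Divide 14.76 by the number of possible onset days, with onset assumed uniform over the window:

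| Assumed onset window (days after first injection) | Onset days | Misdated, `gt` | Misdated, `ge` |
|---|---|---|---|
| 0–30 | 31 | 47.6% | 0% |
| 0–60 | 61 | 24.2% | 0% |
| 0–90 | 91 | 16.2% | 0% |
| 0–182 | 183 | 8.1% | 0% |
| 0–364 | 365 | 4.0% | 0% |

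For scale, if there were 10 such AEs (an assumption), 0.4 to 4.8 would be misdated.

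**Effect on a table row.** One patient is 1/25 = 4.0 percentage points of an arm, or 1/23 = 4.3 points, using the two group sizes in SAP 3. This applies only if that patient has no other qualifying event in the row.

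**What `ge` does to screening events.** With true onset 1 to 14 days before the injection there are 549 × 14 = 7,686 date pairs, of which 5,796 (75.4%) fall in the injection month. Under `ge` all 5,796 become treatment-emergent unless an earlier end date is known; under `gt` none do.

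**Why `ge` alone is not enough.** If a same-month screening event ended before the injection, `ge` dates its start to the injection, which is after its end. This happened in 39,375 of 39,375 enumerated cases, and in 0 once an end-date condition was added. The condition cannot remove a true post-injection event: its known end date cannot precede the injection, and an end date imputed in or after the injection month never does.

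**The case against.** The strongest reply is that no effect has been shown. Nothing in the documents says that any AE has a partial start date, and several provisions make this uncommon: start and end dates are to be recorded, AEs are sought at each four-weekly visit, missing values are queried, SAEs are reported within 24 hours, and symptoms of inflammation should lead to examination within 12 hours. The events that matter most are the least likely to lack a day. This stands as a limit on size; the percentages above are shares of a set that may be empty.

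Second, bias between arms should be small. Both arms receive the same single baseline injection, and the loading arm's second injection comes at week 4, at least 21 days later, so exposure is the same for most of the affected window. This also stands. The tables would under-count events rather than clearly favour one regimen.

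Third, misdated events remain visible in listings, a pre-existing event that worsened may still count, there is no formal safety hypothesis, and all analyses are descriptive. All true, but the incidence tables are the reported result for a secondary endpoint, and a listing does not replace a count.

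Fourth, the end-date rule in the same section uses an inclusive comparison: "if month/year(first injection) le month/year(end date) le month/year(last injection+30) than impute". This might be read as evidence that the start rule was meant to match. It is weak evidence, because for an end date in the first-injection month the neighbouring branch would give the same date: first injection + 30 days is never earlier than the last day of that month. The inactive `max()` is sufficient on its own.

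**Conclusion.** The rule is wrong as written. Read literally, it classes a new post-injection AE as pre-treatment whenever the start day is missing, the start month is the first-injection month and the injection was not on the 1st. It should be corrected. The exposed window averages 14.8 days per patient, and the misdated share of post-injection AEs with a missing start day is 4.0% to 47.6%, depending on the assumed onset pattern. These figures rest on injection dates spread evenly over July 2021 to December 2022 and onset uniform within each window; the number of affected AEs is unknown. The primary endpoint is untouched. No effect on the concomitant-medication summaries is shown, since SAP 2.4.2 covers medication both before and after treatment start.

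**What to change.** Rewrite the start-date rule in SAP 5.1.2, and the program, in this order:

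1. Impute the AE end date first.
2. If the start day is missing and month/year(start) `ge` month/year(first injection), impute the later of the first-injection date and the 1st of the start month. Exception: if the known or imputed end date is before the first injection, impute the 1st of the month.
3. Otherwise impute the 1st of the month, as now.

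Add a sentence to SAP 5.1.3 saying whether the changed start rule carries over to concomitant medication. If the program already uses `ge`, correct the text so that the two agree, and check that the end-date condition is in place.

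The cost is one operator, one condition and one sentence. The downside is that screening events in the first-injection month with a missing start day and no end date before the injection will count as treatment-emergent. That over-counts rather than under-counts, and the SAP should say so.
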